- In **Standby** mode set the initial energy level (startup set recommendations: 30 watts, 90 mJ Pulse energy, 2 stacking, 8x8 pattern. According to the patient's reaction, you can increase up 120 mJ pulse energy and 3 stacking max, pulse mode or repeat mode). **WARNING:** Do not apply energy when inserting the handpiece.
- Insert the handpiece as distally as possible, with the laser energy window oriented to the 12:00 o'clock position. NOTE: There are position markings on the handpiece.
- Set the system to **Ready** mode.
- Trigger a laser pulse by pressing the footswitch.
- Shoot the laser and rotate the probe to each of the 7 numbered increments.
- When you reach the 12:00 o'clock position again, withdraw the handpiece by approximately one centimeter and repeat the rotation treatment procedure.
- Continue pulling back at one centimeter intervals triggering pulses until the handpiece window reaches the entrance of the vagina. Once you reach the entrance of the vagina, stop the treatment.
- Repeat the entire process by 3 passes.
- Repeat if required. NOTE: If necessary, increase or decrease the power to between 80 to 120 MJ, depending on patient comfort.

6.5.5 Clinical End-Points:

The clinical end point is determined when the entire treatment process described above has been completed.

6.5.6 Post Treatment Care:

Following treatment:

Post treatment care: immediately after treatment, patient will refrain from inserting anything into the vagina for 7 days. The patient will be provided with Lidocaine Ointment 5% to apply to outside of vagina every 4 hours as needed for the next 1-2 days.

Subjects must be instructed to avoid vaginal estrogen therapy during, pre- and post-operative period.

If adverse side effects occur the patients will call [name] at [contact] and [contact]

6.6 Premature Discontinuation from Study

A subject may be withdrawn from the study at any time at either the Investigator's or the subject's discretion.

Participation in this research study may be discontinued for any of the following reasons:

1. Normal protocol completion.
2. Severe adverse reactions.
3. Noncompliance with protocol requirements (consistently missed study visits).
4. Subject requests to withdraw from study for whatever reason.

The reason for discontinuance from the study will be documented in the CRF.

Discontinued subjects will be asked to come in for a 1 month follow up after the last treatment.

6.7 Treatment Modification/Toxicity Management

In the event of severe irritation, vaginal bleeding, pain, discomfort, or infection treatment will be stopped. A patient may also discontinue if they cannot tolerate the discomfort that occurs during the treatment. A subject may be removed from the study for untoward or severe adverse reactions at the discretion of the study physician.

6.8 Compliance

At each treatment visit, subjects will be questioned regarding their compliance with the study protocol. Those subjects who consistently miss treatments or study visits, or who use con meds/therapies will be discontinued. Each treatment will be followed up between 30 – 45 days from the previous treatment.

7. STUDY ASSESSMENTS

7.1 Investigator Assessment- Clinical Improvement Evaluation

At baseline, before each treatment and before each follow-up visit, the investigator will evaluate the clinical improvement from the visual appearance of the treated area using a visual analogic scale (10 cm VAS).

8.0 DATA COLLECTION AND ANALYSIS

8.1 Recording of Data

The CRFs for each subject will be created by the research team. All CRFs are to be completed by the personnel administering the tests. All forms must be completed in black ink or typed. If an entry is blank because the item was not done, mark the item not done. If the item is unknown, mark the item UNK. If the item is not applicable to the subject, mark the space N/A. Corrections of data on the CRFs can be made only by crossing out the incorrect data with a single horizontal line and writing the correct values next to those crossed out. Each correction must be initialed and dated by the person making the correction. If corrections are made after review and signature by the Investigator, the Investigator must so document by initialing and dating the changes.

The CRFs will be reviewed by the Investigator who will sign the last page to acknowledge that review. The original completed CRF will be retained by the Sponsor, Perigee Medical.

8.2 Statistical Methods

8.2.1 Population

All subjects who receive treatment and complete the study will be considered evaluable.

8.2.2 Statistical and Analytical Plan (sponsor responsibility)

Upon completion of the research study, the data will be analyzed for tolerance and efficacy at each follow-up interval versus baseline. Only those subjects who satisfy the criteria for an “evaluable subject” will be included in the statistical analysis of efficacy. An evaluable subject is one who meets all entry criteria, not used any unapproved medications or therapies during the study, completed the follow-up visits and evaluations, and complied with the treatment regimen.

Adverse reactions during the study will be summarized using descriptive statistics and percentages whenever it is appropriate. The primary objective of this study is to assess the safety and efficacy of the CO₂ fractional handpiece in the treatment of vulvovaginal atrophy. The primary efficacy endpoint is the change from baseline in the vaginal dryness as determined by a visual analogic scale (10 cm VAS).

9.0 ADVERSE EVENTS

9.1 Introduction

All adverse events occurring during the course of a study will be documented on Adverse Event Forms. A separate Adverse Event Form will be filled out for each adverse event. All items on the form will be completed. For NONSERIOUS events, if information is missing at the initial visit and the subject will be returning for follow-up examination in a reasonably short period of time, the investigator may hold the Adverse Event Form until the scheduled follow-up examination. If the subject will not be returning in a reasonable period of time, the investigator will forward the form to the Sponsor and provide the missing information by letter or telephone call when the information is known. For SERIOUS adverse events, an Adverse Event Form will be returned to the Sponsor as soon as practical, even if it is incomplete, with new information submitted by telephone call as soon as it becomes known.

9.2 Nonserious Adverse Event

An adverse event is defined as any untoward medical occurrence in a patient, or clinical investigation subject, undergoing a test treatment whether or not it is caused by this treatment. An adverse event can, therefore, be any unfavorable and unintended sign, symptom or disease temporarily associated with the use of a device, whether or not considered related to the device.

Events that occur prior to the use of the light device are not considered adverse events.

A non-serious adverse event is defined as a change in a subject's medical health, which is neither life threatening, does not require hospitalization, does not prolong a current hospitalization, and is not disabling.

Possible expected occurrences due to the use of the Edge fractional CO₂ laser may include the following reactions which will not be reported as adverse events:

- **Heating sensation or pain** – subject may experience a heating sensation during or just following the treatment, however, such pain is expected to be mild and to resolve within few minutes.
- **Burns**
- **Chronic Urinary tract infection**
- **Vaginal infections**
- **Moderate to severe vaginal bleeding (more than a menstrual period)**

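### Section 9.2 exempts burns, infections and heavier bleeding from adverse-event reporting, against its own definition, and leaves their place in the safety summary unclear

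*Protocol*

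**What the plan says.** Section 9.2 opens with a wide definition. An adverse event is "any untoward medical occurrence in a patient, or clinical investigation subject, undergoing a test treatment whether or not it is caused by this treatment". Section 9.1 adds the recording rule: "All adverse events occurring during the course of a study will be documented on Adverse Event Forms", with a separate form for each event.

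Further down, section 9.2 names five possible occurrences from the laser and states that these "may include the following reactions which will not be reported as adverse events". They are heating sensation or pain, burns, chronic urinary tract infection, vaginal infections, and bleeding heavier than a period. Of the first it says that "such pain is expected to be mild and to resolve within few minutes". The other four carry no such description, and the bleeding item is exempted explicitly at the upper grades: "Moderate to severe vaginal bleeding (more than a menstrual period").

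Three other places bear on this:

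- Section 8.2.2 on aims: "The primary objective of this study is to assess the safety and efficacy". Section 3 likewise names safety.
- Section 8.2.2 on the safety output: "Adverse reactions during the study will be summarized using descriptive statistics and percentages whenever it is appropriate".
- Section 6.7 on stopping: "In the event of severe irritation, vaginal bleeding, pain, discomfort, or infection treatment will be stopped".

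**The concern.** The exempted reactions are the harms that the protocol itself expects from the device. Section 4 says the handpiece is a variant without FDA clearance, so its safety profile is one of the things the study is meant to establish. If the listed reactions never reach an Adverse Event Form, a safety table built from those forms will understate them. If the table is built from Case Report Form notes instead, the reactions may be counted, but without the per-event completeness and forwarding rules that section 9.1 attaches to adverse events. Two analysts following the text could therefore report different safety results for the same subjects. The investigator's summary under section 10.9, which covers the occurrence of adverse events, is exposed in the same way.

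**Working it through.** The finding rests on the text. No figure in the plan has to be reproduced.

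**Step 1: the rules side by side.** The definition in 9.2 makes no exception for expected or device-related events. The rule in 9.1 covers all adverse events. The exemption in 9.2 takes five kinds of event out of reporting. A burn or a vaginal infection after treatment meets the definition, so 9.1 requires a form for it, while the exemption says it is not reported as an adverse event.

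**Step 2: the five items.** The last column compares each item with the stopping list in 6.7.

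| Listed reaction (9.2) | Severity or duration limit given | Kind of event named in 6.7 |
|---|---|---|
| Heating or pain | Yes: mild, lasting minutes | Pain, depending on reading |
| Burns | None | Not named |
| Chronic urinary tract infection | None | Infection |
| Vaginal infections | None | Infection |
| Bleeding | No upper limit; moderate to severe | Vaginal bleeding |

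- Items without an upper limit: 5 − 1 = 4 of 5.
- Items of a kind named in 6.7: up to 4 of 5. If the word severe in 6.7 governs its whole list, mild pain drops out, leaving 4 − 1 = 3 of 5. The two infections and the bleeding remain, because the exemption covers their severe forms too.

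The overlap with 6.7 is a tension and not a contradiction, because a reaction can stop treatment without being called an adverse event. It does show that a reaction grave enough to end treatment may need no Adverse Event Form.

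**Step 3: other recording routes.**

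- The Synopsis and section 5.1 have side effects documented in the Case Report Form.
- Section 6.2 has strong reactions documented there.
- Section 6.6 records the reason for discontinuation.
- Section 9.3 opens with a wide clause on any finding that suggests a significant hazard or side effect. Its outcome criteria (such as hospitalisation) attach to any adverse event, which the listed reactions are said not to be reported as. Serious cases can reach the sponsor, though the wording is not fully secure.

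None of these routes requires an Adverse Event Form for a non-serious listed reaction, and none is linked to the summary in 8.2.2.

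**Step 4: illustration of size.** The protocol gives no expected rates, so the per-subject rates *p* of any non-serious listed reaction are assumptions. Expected number affected = *np*; chance of at least one = 1 − (1 − *p*)^*n*, treating subjects as independent. Section 6.2 gives up to 30 subjects; section 5.2 gives up to 25 evaluable.

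| Assumed *p* | *n* = 30: expected | *n* = 30: at least one | *n* = 25: expected | *n* = 25: at least one |
|---|---|---|---|---|
| 5% | 1.5 | 1 − 0.95^30 = 78.5% | 1.25 | 1 − 0.95^25 = 72.3% |
| 10% | 3 | 1 − 0.90^30 = 95.8% | 2.5 | 1 − 0.90^25 = 92.8% |
| 20% | 6 | 1 − 0.80^30 = 99.9% | 5 | 1 − 0.80^25 = 99.6% |

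The columns for 30 matter more, since safety concerns everyone treated and 8.2.2 applies the evaluable restriction to the efficacy analysis.

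**The case against.** The strongest reply is that the data are not lost. The Case Report Form is itself required, side effects must be documented in it, and the visit schedule in 6.4.1 has an adverse-side-effects row at every treatment visit and the first three follow-ups. Section 8.2.2 speaks of adverse reactions and 9.2 calls the exempted items reactions, so a summary that counts them is at least as natural a reading as one that leaves them out. How the table is built may also be settled in a statistical analysis plan that is not at hand. Finally, the rates in the illustration are chosen and not drawn from the protocol.

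Much of this stands, and it limits the claim. The place of these reactions in the summary is unclear; they are not shown to be excluded. The illustration says only that affected subjects are likely at the assumed rates. But the reply does not remove the conflict between the exemption, the definition in 9.2 and the rule in 9.1, and no other section cancels the exemption. Nor can an analysis plan cure it: the exemption is a data-capture rule, and later analysis cannot restore forms that were never completed.

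**Conclusion.** The concern holds. Section 9.2 contradicts its own definition and section 9.1. For 4 of the 5 exempted reactions nothing confines the exemption to trivial cases. Followed as written, it keeps non-serious device harms off the Adverse Event Form in a study whose primary objective includes safety. The consequence for the 8.2.2 summary is ambiguity, and understatement if the summary is drawn from Adverse Event Forms. The contradiction needs no assumed rate; the number of subjects affected does, and the protocol offers none. This must be fixed, and before data are collected, because incomplete capture is hard to repair afterwards.

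**What to change.** - In 9.2, delete the clause that takes the listed reactions out of adverse-event reporting. State instead that they are anticipated adverse events, recorded on the Adverse Event Form with severity, relatedness and outcome.
- In 8.2.2, state that they are included in the safety summary for all treated subjects.
- Use the single term adverse events in 8.2.2, 9.1 and 9.2.
- Reconcile 9.2 with 6.7 as to recording only. Nothing here proposes a change to when treatment stops.
- As a separate minor correction, mark the adverse-event row at the month-4 visit in the 6.4.1 schedule, since 6.4.4 lists an adverse-event evaluation for the follow-up visits, including month 4.

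The cost is a protocol amendment and a few more forms, with no extra visits or staff. If listed reactions occur and would otherwise have been left out, the adverse-event table will look less favourable.

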9.3 Serious Adverse Event

Serious adverse events are defined as any finding which suggests a significant hazard, contraindication, side effect, or precaution. Additionally, any adverse event which results in a fatality, is life threatening, is permanently disabling, requires inpatient hospitalization, prolongs a current hospitalization, or a congenital anomaly is also considered a serious adverse event.

A life threatening adverse event means that the subject was, in the view of the investigator, at immediate risk of death from the reaction as it occurred. It does not include a reaction that, had it occurred in a more serious form, might have caused a death. Serious, alarming and/or unusual adverse events must be reported to the following individual within 24 hours of the investigator's knowledge of the event:

CONTACT: [name]
[name]
[name]
[contact] Exchange
[contact](mobile)
E Mail: [contact] – non urgent and non HIPPA compliant

An Adverse Event Form will be completed for all serious adverse events and forwarded to the Sponsor within 24 hours. Additionally, a phone call will be made to confirm delivery of the report. When new significant information is obtained as well as when outcome of an event is known, the Sponsor will be informed by telephone call. Depending on the nature and seriousness of the adverse event, a copy of the medical record of the patient as well as results of laboratory tests performed may be requested. If the subject was hospitalized, a copy of the discharge summary may be forwarded to the Sponsor as soon as it is ready. In all instances, investigators will follow subjects until an outcome to the event is known.

10.0 ADMINISTRATIVE REQUIREMENTS

10.1 Principal Investigator

The Principal Investigator is responsible for insuring the investigation is conducted according to the study protocol and good clinical practice guidelines.

10.2 Study Coordinator

The study coordinator is the contact person at the investigational site who is appointed by the Principal Investigator to assure that all elements of the protocol are faithfully implemented.

10.3 Informed Consent and Institutional Review Board

All subjects in this study will be completely informed, according to informed consent guidelines, about the pertinent details and purpose of the study. A written Informed Consent form will be understood and signed by each subject prior to enrollment into the study. The investigator or his designee will supply the consent form, approved by an Institutional Review Board, and a copy of such provided to the Sponsor. The study site will keep the original signed copies of all consent forms in its files and will provide the subject with a duplicate copy.

This study must be reviewed and approved by an appropriate Institutional Review Board (also known as an Ethics Committee). A copy of the letter indicating IRB approval will be provided to the Sponsor prior to study initiation. Annual updates will be provided to the IRB by the investigator for studies longer than a year. This study will not last more than 1 year.

10.4 Adherence to Protocol

The Investigator is not permitted to deviate from the protocol without proper notification of the Sponsor. Except for an emergency situation in which proper care for the protection, tolerance

and well being of the study subject requires alternative treatment, the study shall be conducted exactly as described in the approved protocol. Any deviation from the protocol must be reported, explained, and documented in the CRF.

10.5 Protocol Amendment

Should amendments to the protocol be required, the amendment must be reviewed and approved by the Sponsor. The written amendment to the Study Protocol must be submitted to the chairperson of the IRB responsible for overseeing the conduct of this study. This amendment must be approved by the IRB prior to its implementation.

10.6 Data Collection

The research facility will maintain detailed records on all study subjects. Data for this study will be recorded on Case Report Forms (CRFs). All data will be recorded completely, promptly, and legibly on the CRFs. Corrections will be made in a manner that does not obscure or eliminate the original error, by striking through the original data with one line, and all corrections on the CRF should be initialed and dated. The testing facility will maintain a copy of all completed CRFs in its study files.

10.7 Test Device Accountability

The principal investigator or his designee, upon receipt of the CO2 fractional handpiece module, will conduct an inventory and complete and sign the Receipt of Clinical Supplies form (Supplied by the Sponsor), mailing it to the Sponsor. A copy will be maintained for the investigator's records.

The clinical staff will keep a current record of the date and time of the use of the module. Additionally, the clinical staff will confirm on the subject's data sheet (or CRF) the date and time of the module use. These records will be made available to the Sponsor's monitor for the purpose of accounting for all clinical supplies. Any significant discrepancy and/or deficiency will be recorded, with an explanation. After all subjects have completed the study, the testing facility will return the CO2 fractional handpiece to the Sponsor with a copy module use log.

10.8 Study Monitoring

The study may be monitored at any time. The monitor from the Sponsor will maintain a close liaison with the research facility to clarify any problem(s) that may arise in the study and to ensure that the study is conducted according to the protocol. The liaison ordinarily consists of personal visits and/or frequent communications via telephone, fax and/or email.

The investigator will allow a Sponsor monitor to inspect all Case Report Forms and corresponding portions of a study subject's records, if necessary, to verify that the study was performed according to this protocol and that test results and collected data were faithfully and accurately recorded.

10.9 Information Reporting Responsibilities of Investigator

The Investigator will be responsible for producing a summary of the study that will detail the conduct of the study, protocol deviations, and occurrence of adverse events and any ancillary reports or statistical data generated by the Investigator's team.

10.10 Confidentiality

Subjects will be identified on the study CRFs by their Subject Number and their initials. CRFs are confidential documents and will only be available to the Investigator, the sponsor's

representative, and the IRB. Individual subject's medical information obtained as a result of this study is considered confidential, and disclosure to third parties is prohibited according to federal HIPAA regulations.

10.11 Record Retention

All records relating to the conduct of this study will be held by the investigator for a period of no less than six (6) years in a secure area. Additionally, the Sponsor will be contacted prior to the destruction of any study related records. Should the Sponsor require archiving for longer than 6 years, prior agreement between the Site and the Sponsor must be obtained.
